9.1.2. Assessment of Severity

The investigator will assess the severity of each AE and SAE reported during the study. AEs and SAEs should be assessed and graded based upon the NCI-CTCAE Version 4.03 or higher.

Toxicities that are not specified in the NCI-CTCAE will be defined as follows:

- Grade 1: Mild; asymptomatic or mild symptoms; clinical or diagnostic observations only; intervention not indicated
- Grade 2: Moderate; minimal, local, or noninvasive intervention indicated; limiting age-appropriate instrumental activities of daily living
- Grade 3: Severe or medically significant but not immediately life-threatening; hospitalization or prolongation of hospitalization indicated; disabling; limiting self-care activities of daily living
- Grade 4: Life-threatening consequences; urgent intervention indicated
- Grade 5: Death related to an AE

Note: The terms “severe” and “serious” are not synonymous. Severity is a measure of intensity (eg, grade of a specific AE, mild [Grade 1], moderate [Grade 2], severe [Grade 3], or life-threatening [Grade 4]); whereas, seriousness is classified by the criteria based on the regulatory definitions. Seriousness serves as the guide for defining regulatory reporting obligations from the sponsor to applicable regulatory authorities as described in [Section 9.5](#).

9.1.3. Assessment of Causality

The investigator is obligated to assess the relationship between pamiparib and the occurrence of each AE or SAE using best clinical judgment. Alternative causes, such as natural history of the underlying diseases, concomitant therapy, and other risk factors, and the temporal relationship of the AE or SAE to pamiparib will be considered and investigated. The investigator should consult the [Pamiparib Investigator’s Brochure](#) in the determination of his/her assessment. There may be situations when an SAE has occurred and the investigator has minimal information to include in the initial report to the sponsor. However, it is very important that the investigator always provides an assessment of causality for every SAE before transmission of the SAE report/eCRF to the sponsor because the causality assessment is one of the criteria used when determining regulatory reporting requirements. The investigator may change his/her opinion of causality based on follow-up information, amending the SAE report/eCRF accordingly.

The causality of each AE should be assessed and classified by the investigator as “related” or “not related.” An AE is considered related if there is at least “a reasonable possibility” that the AE may have been caused by pamiparib (ie, there are facts, evidence, or arguments to suggest possible causation, or a causal relationship between the AE and the drug cannot be ruled out). A number of factors should be considered in making this assessment, including:

- Temporal relationship of the AE to the administration of pamiparib/study procedure
- Whether an alternative etiology has been identified
- Mechanism of action of pamiparib
- Biologic plausibility

An AE should be considered “related” to pamiparib if any of the following are met, otherwise the event should be assessed as “not related”:

- There is clear evidence to suggest a causal relationship, and other possible contributing factors can be ruled out
- There is evidence to suggest a causal relationship, and the influence of other factors is unlikely
- There is some evidence to suggest a causal relationship (eg, the AE occurred within a reasonable time after administration of pamiparib). However, the influence of other factors may have contributed to the AE (eg, the patient’s clinical condition or other concomitant AEs).
- A causal relationship between the AE and the study drug cannot be ruled out

9.1.4. Follow-Up of Adverse Events

After the initial AE or SAE report, the investigator is required to proactively follow each patient and provide further information to the sponsor on the patient’s condition.

All AEs and SAEs documented at a previous visit/contact and designated as ongoing will be reviewed at subsequent visits/contacts.

All AEs and SAEs will be followed until resolution, the condition stabilizes or is considered chronic, the AE or SAE is otherwise explained, the patient is lost to follow-up, or the patient withdraws consent. Once resolved, the appropriate AE or SAE eCRF page(s) will be updated. The investigator will ensure that follow-up includes any supplemental investigations as may be indicated to elucidate the nature and/or causality of the AE or SAE. This may include additional laboratory tests or investigations, histopathologic examinations, or consultation with other health care professionals.

The sponsor may request that the investigator perform or arrange for the conduct of supplemental measurements and/or evaluations to elucidate as fully as possible the nature and/or causality of the AE or SAE. The investigator is obligated to assist. If a patient dies during participation in the study or during a recognized follow-up period, the sponsor will be provided with a copy of any postmortem findings, including histopathology if conducted.

New or updated information will be recorded on the originally completed SAE report/eCRF, with all changes signed and dated by the investigator. The updated SAE follow-up report/eCRF should be resent to the sponsor within the timeframes outlined in [Section 9.5.1](#).

9.1.5. Laboratory Test Abnormalities

Abnormal laboratory findings (eg, chemistry, hematology, or coagulation) or other abnormal assessments (eg, ECGs, x-rays, or vital signs) that are judged by the investigator as clinically significant will be recorded as AEs or SAEs. This includes clinically significant abnormal laboratory findings or other abnormal assessments that are present at baseline and significantly worsen during the study. The definition of clinically significant is entrusted to the judgment of the investigator. In general, these are the abnormalities that:

- Are associated with clinical signs or symptoms, or

- Require active medical intervention, or
- Lead to dose interruption or discontinuation, or
- Require close observation, more frequent follow-up assessments, or
- Further diagnostic investigation

9.2. Definition of a Serious Adverse Event

An SAE is any untoward medical occurrence that, at any dose:

- Results in death
- Is life-threatening

Note: The term “life-threatening” in the definition of “serious” refers to an AE in which the patient was at risk of death at the time of the AE. It does not refer to an AE that hypothetically might have caused death if it was more severe.

- Requires hospitalization or prolongation of existing hospitalization

Note: In general, hospitalization signifies that the patient was admitted (usually involving at least an overnight stay) to the hospital or emergency ward for observation and/or treatment that would not have been appropriate in the physician’s office or outpatient setting. Complications that occur during hospitalization are AEs. If a complication prolongs hospitalization or fulfills any other serious criteria, the AE is serious. When in doubt as to whether “hospitalization” occurred or was necessary, the AE should be considered serious.

- Results in disability/incapacity

Note: The term disability means a substantial disruption of a person’s ability to conduct normal life functions. This definition is not intended to include experiences of relatively minor medical significance, such as uncomplicated headache, nausea, vomiting, diarrhea, influenza, and accidental trauma (eg, sprained ankle), which may interfere with or prevent everyday life functions but do not constitute a substantial disruption.

- Is a congenital anomaly/birth defect
- Is considered a significant medical AE by the investigator based on medical judgment (eg, may jeopardize the patient or may require medical/surgical intervention to prevent one of the outcomes listed above)

The following are NOT considered SAEs:

- Hospitalization for elective treatment of a preexisting condition that did not worsen from baseline
- Hospitalization for social/convenience considerations
- Scheduled therapy for the target disease of the study, including admissions for transfusion support or convenience

9.3. Timing, Frequency, and Method of Capturing Adverse Events and Serious Adverse Events

9.3.1. Adverse Event Reporting Period

After the ICF has been signed, but before initiation of pamiparib, only SAEs should be reported to the sponsor.

After initiation of treatment, all AEs and SAEs, regardless of relationship to treatment, will be reported until 30 days after the last dose of pamiparib or initiation of new anticancer therapy, whichever occurs first. After this period, the investigator should report any SAEs that are believed to be related to prior study drug treatment.

After a patient is discontinued from the study, investigators are not obligated to actively seek AEs or SAEs from the former patients. However, if the investigator learns of any SAE, including a death, at any time, and considers the SAE related to pamiparib, the investigator will notify the sponsor.

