1.8. Risk-Benefit Assessment

Pamiparib has been studied in nonclinical toxicity and Phase 1 clinical studies. Pamiparib toxicities are largely consistent with the safety profile shared by other PARP inhibitors. The safety profile and adverse drug reactions observed in patients treated with pamiparib monotherapy are summarized in Section 6, Summary of Data and Guidance for the Investigator of the [Pamiparib Investigator's Brochure](#).

MDS and AML have been reported in a small number (< 1%) of patients treated with PARP inhibitors, especially in patients harboring a germline BRCA mutation ([Ricks et al 2015](#)). Typically, patients who develop MDS and AML while on therapy with a PARP inhibitor have a history of extensive previous chemotherapy and some have a history of previous cancer or bone marrow abnormalities. To date, there have been no reports of MDS or AML in patients treated with pamiparib and no fatal adverse drug reactions. Patients in this study will be monitored monthly for hematologic toxicities and events of MDS and AML will be reported as SAEs.

Preliminary data from ongoing monotherapy studies show that pamiparib appears to be generally well tolerated in patients with advanced solid tumors. The safety profile for single-agent pamiparib is similar to those observed in other PARP inhibitors. Some antitumor activity has been observed across the dose ranges evaluated in patients. Therefore, the risk-benefit profile for pamiparib monotherapy is considered acceptable in a patient population with metastatic cancer.

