5.6.2. Long-term Follow-up

Patients will be followed for survival and initiation of new anticancer therapy via telephone contact or other means (eg, clinic visit) approximately every 12 weeks ([Appendix 1](#)).

Patients who do not have objective disease progression at the time of pamiparib permanent discontinuation but meet other discontinuation criteria (eg, discontinued for AE and no new anticancer therapy) will continue to have tumor and PSA assessments every 12 weeks and 4 weeks (± 7 days), respectively, until PD or any other reason listed in [Section 5.6.4](#), whichever occurs first. For efficacy assessments as per protocol, refer to [Section 7.3](#) and [Appendix 1](#). If the patient refuses to return for these PSA and tumor assessments or is unable to do so, every effort should be made to contact the patient by telephone to determine the patient's disease status and survival.

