6.1.4. Dose Hold and Modification

AEs should be assessed as best as possible regarding their relatedness to pamiparib. Patients should continue on study with follow-up as outlined in [Sections 5.5](#) and [5.6](#).

Investigators should make every effort to maintain dose intensity in patients. Dosing of pamiparib can be withheld for up to 28 days consecutively. Dose reductions are allowed in 20 mg per dose decrements. If drug is held \geq 28 days, the medical monitor must be contacted before permanent patient discontinuation from pamiparib.

Criteria for treatment modifications and suggested guidelines for the management of some toxicities related to pamiparib are summarized below. These general guidelines may be modified at the discretion of the investigator based on discussions with the medical monitor and the best clinical judgment at that time; any decisions should be documented. Any toxicities related to pamiparib should be managed according to standard medical practice.

A maximum of 2 dose reductions is allowed before the patient must be permanently withdrawn from pamiparib. Dose levels for pamiparib are summarized in [Table 3](#). Pamiparib will be dose modified as outlined in [Table 4](#). For prolonged hematologic toxicities, interrupt treatment and monitor blood counts weekly until recovery. If the levels have not recovered to NCI-CTCAE Grade 1 or less after 4 weeks, further investigations should be considered, including bone marrow analysis and blood sample for cytogenetics. If MDS or AML is confirmed, discontinue pamiparib.

Table 3: Dose Levels for Pamiparib

Dose Level	Pamiparib
1	60 mg orally twice a day
-1	40 mg orally twice a day
-2	20 mg orally twice a day

Pamiparib may be dose-reduced for a maximum of 2 dose reductions.

Table 4: Criteria for Modification of Pamiparib Dosing for Related Adverse Events

Toxicity		Recommended Dose Modification ^a
Hematologic		
Anemia (hemoglobin)		
Hgb < 9.0 g/dL		
 • First occurrence of Hgb < 9.0 g/dL: Hold pamiparib and treat as medically indicated to get Hgb to \geq 9 g/dL, and then ↓ pamiparib by 1 dose level to 40 mg BID
Grade 2 (Hgb <10 - 8 g/dL)	Hgb <10 - 9 g/dL	Continue dosing at current dose level and treat with appropriate supportive care as medically indicated

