10.5.2. Adverse Events

The AE will be coded using Medical Dictionary for Regulatory Activities Version 20.0 or higher and graded using NCI-CTCAE Version 4.03 or higher.

A TEAE is defined as an AE that had an onset date on or after first dose of pamiparib or was worsening in severity from baseline (pretreatment) up to 30 days following permanent discontinuation of pamiparib or initiation of new anticancer therapy, whichever occurs first. All TEAEs will be included in summary tables and in-patient data listings.

The incidence of TEAEs will be reported as the number (percentage) of patients with TEAEs by system organ class and preferred term. A patient will be counted only once by the highest grade according to NCI-CTCAE Version 4.03 or higher within a system organ class and preferred term, even if the patient experienced more than one TEAE within a specific system organ class and preferred term. The number (percentage) of patients with TEAEs will also be summarized by relationship to the study treatment. Treatment-related AEs include those events considered by the investigator to be related to study treatment or with missing assessment of the causal relationship. SAEs, deaths, TEAEs \geq Grade 3, pamiparib-related TEAEs, and TEAEs that led to pamiparib withholding or permanent discontinuation will also be summarized.

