### 6.5.2 Adverse Events

AEs will be graded by the investigators using CTCAE v4.03. The AE verbatim descriptions (investigator terms from the CRF) will be classified into standardized medical terminology using the Medical Dictionary for Regulatory Activities (MedDRA) Version 20.0 or higher.

A treatment emergent adverse event (TEAE) is defined as an AE that had an onset (including worsening from pretreatment) date on or after the first dose of study treatment through 30 days after the last dose of study treatment or initiation of new anti-cancer therapy, whichever occurs first. Only TEAEs will be included in summary tables. All AEs, treatment emergent or otherwise, will be presented in patient data listings.

An overview table, including the number and percentage of patients with TEAEs, serious TEAEs, grade 3 or higher TEAEs, treatment-related TEAEs, TEAEs that led to death, and TEAEs that led to treatment discontinuation, dose reduction or dose interruption will be provided. Treatment-related TEAEs include those events considered by the investigator to be related to study treatment or with missing assessment of the causal relationship.

The incidence of TEAEs will be reported as the number and percentage of patients with TEAEs by SOC and PT. A patient will be counted only once by the highest severity grade within an SOC and PT, even if the patient experienced more than 1 TEAE within a specific SOC and PT. The number and percentage of patients will be summarized by SOC and/or PT for the following:

- TEAEs

- Treatment Related Grade 3 or higher TEAEs
- Serious TEAEs
- TEAEs that led to treatment discontinuation
- TEAEs that led to dose modification

TEAEs will also be summarized by PT in descending order. A listing of all AEs and AEs that led to treatment discontinuation will be provided.

All deaths and causes of death will be provided in a listing, including those occurring during the study treatment period and those reported during the survival follow-up period after treatment completion/discontinuation.

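### Late MDS/AML could be under-ascertained, because once all-cause reporting ends only SAEs believed related are required; separately, the 30-day TEAE window has two different anchors

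*Protocol*

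**What the plan says.** **The stated intention.** Protocol 1.8 names MDS and AML as a risk reported in under 1% of patients on PARP inhibitors, typically after extensive chemotherapy. It says that "events of MDS and AML will be reported as SAEs".

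**The reporting rule.** Under Protocol 9.3.1, all AEs and SAEs "will be reported until 30 days after the last dose of pamiparib or initiation of new anticancer therapy, whichever occurs first". The next sentence reads: "After this period, the investigator should report any SAEs that are believed to be related to prior study drug treatment". Appendix 1 footnote o repeats the rule. Neither place mentions MDS or AML.

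**What happens after the window.** Protocol 5.6.2 states: "Patients will be followed for survival and initiation of new anticancer therapy via telephone contact or other means". The interval is about 12 weeks, and patients without progression also have tumor and PSA assessments. In Appendix 1 the hematology row stops at Safety Follow-up. The adverse-event row is marked under long-term follow-up, but footnote o governs what is reported there.

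**What is tabulated.** The SAP (6.5.2) says: "Only TEAEs will be included in summary tables". Its listings hold all AEs, and deaths during survival follow-up are listed with cause.

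**The TEAE window.** Protocol 10.5.2 runs it "up to 30 days following permanent discontinuation of pamiparib or initiation of new anticancer therapy, whichever occurs first". SAP 6.5.2 runs it to 30 days after the last dose, with the same cut at new anticancer therapy.

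**The concern.** Section 1.8 reads as an unconditional commitment, while the operative rule in 9.3.1 makes reporting of a late case depend on the investigator's causality judgment. That judgment is not simple here. Inclusion criterion 11 requires a prior taxane for every patient, and many will go on to another therapy, so there is usually another possible cause. Starting that next therapy also closes the all-cause window.

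What is at stake is how a report of no MDS/AML would be read. It would cover time on drug plus about 30 days, and beyond that only events that came to light and were judged related. It could not be read as a rate over the follow-up that patients actually had.

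The second anchor for the TEAE window is a separate matter. The same event can be treatment-emergent under the protocol and not under the SAP, and it is the SAP definition that decides what enters the tables.

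**Working it through.** **Step 1: is a late case reportable?** Reading 9.1.3, 9.1.4, 9.1.5 and 9.3.1 together:

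| Situation | Rule | Result |
|---|---|---|
| Cytopenia that led to an interruption, still open at day 30 | 9.1.5 records it as an AE; 9.1.4 follows it to resolution, stabilization or chronicity, with supplemental investigations | Covered past day 30 |
| New MDS/AML after the window, judged related | 9.3.1, no end date | Reportable |
| New MDS/AML after the window, attributed to earlier or later therapy | 9.3.1 and footnote o | Not required |
| Late case that nobody asks about | 5.6.2 contact covers survival and new therapy; no scheduled hematology | May not come to light |

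The last two rows are the gap. If such a case is collected, its onset lies outside the SAP's TEAE window, so it is listed and not tabulated.

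**Step 2: the TEAE anchors.** Inputs are a hold of up to 28 consecutive days (6.1.4), a 30-day window, and the assumption that permanent discontinuation is dated at the decision to stop, at the end of the hold. Days are counted from the last dose, with no new anticancer therapy.

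- Protocol 10.5.2: 28 + 30 = day 58.
- SAP 6.5.2 and Protocol 9.3.1: day 30.
- Difference: 58 − 30 = 28 days.

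Example: MDS with onset on day 45 is treatment-emergent under the protocol (45 < 58) and not under the SAP (45 > 30). From day 31 to day 58 the protocol's TEAE definition is still open, while 9.3.1 requires only related SAEs.

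**Step 3: how many cases could be involved?** The documents give a rate of under 1%. I assume 0.25%, 0.5% and 1%, with complete ascertainment. The chance of at least one case is 1 − (1 − p)^n.

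| Assumed rate | n = 100 (planned) | n = 13 (enrolled, SAP section 8) |
|---|---|---|
| 0.25% | 22% | 3% |
| 0.5% | 39% | 6% |
| 1% | 63% | 12% |

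**Step 4: what would zero cases show?** The one-sided 95% upper limit is 1 − 0.05^(1/n).

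- n = 100: 1 − 0.05^(1/100) = 2.95%.
- n = 13: 1 − 0.05^(1/13) = 20.6%.

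Both limits assume that every patient was asked throughout the period the statement covers. Neither document states a figure for this point, so there is none to reproduce.

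**The case against.** The strongest reply is that the protocol's other safeguards already do most of the work.

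- Section 9.1.3 calls an event related if a causal link to the drug cannot be excluded, and a contributing factor such as a prior taxane does not by itself make it unrelated. For a recognized class effect, many late cases would qualify.
- Related SAEs stay reportable with no end date, even after a patient leaves the study.
- Patients in long-term follow-up are still on study (5.7), and Appendix 1 marks adverse events there.
- Section 1.8 is a risk-benefit paragraph. It can be read as classifying seriousness, with the reporting period left to 9.3.1.
- Exclusion criterion 4 removes prior platinum, cyclophosphamide and mitoxantrone for prostate cancer, so the heaviest prior exposures are partly screened out.
- With so few cases expected, a listing would show one.

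All of this stands, and it narrows the gap. It does not close it: follow-up under 9.1.4 needs an AE already recorded, the low threshold still needs an attribution, and a listing shows only what was collected.

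Two stronger readings are tempting. A reader might infer that AE collection simply closes at 30 days and MDS/AML would be missed. The points above rule that out. A reader might also set the marrow work-up rule in 6.1.4 ("If the levels have not recovered to NCI-CTCAE Grade 1 or less after 4 weeks, further investigations should be considered") against the 30-day window and see a margin of only 30 − 28 = 2 days. That margin has little consequence. The 4-week clock runs from an interruption for cytopenia, and such a cytopenia is already an open AE that is followed beyond day 30.

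**Conclusion.** The point holds as possible under-ascertainment. Section 1.8 and section 9.3.1 with footnote o are not reconciled: a new MDS/AML after the window that is attributed to other therapy need not be reported, and nothing scheduled looks for it. The number of cases affected cannot be computed from the documents, because it depends on attribution and on what investigators happen to learn.

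The TEAE anchor conflict is a plain inconsistency between Protocol 10.5.2 on one side and Protocol 9.3.1 and SAP 6.5.2 on the other. It reaches about 28 days for a patient stopped after a full 28-day hold. It is smaller for shorter holds, and nil if permanent discontinuation is dated at the last dose, which 10.5.2 does not say.

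Practical weight is low for the trial as conducted. With 13 patients, the chance of any case is 3% to 12% at the assumed rates. A reader might take the 3.0% limit for zero of 100 as this trial's reassurance, but enrollment stopped at 13, where the limit is 20.6% even with complete inquiry. SAP section 8 keeps the safety analyses as planned, so the anchor and the wording of any statement on MDS/AML still matter for the report.

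**What to change.** 1. **Protocol 9.3.1 and Appendix 1 footnotes f and o:** state that MDS and AML are collected regardless of causality or new anticancer therapy through long-term follow-up, by one question at the existing 12-weekly contact, and reported on the SAE form. This reconciles these places with 1.8.
2. **SAP 6.5.2:** add one line counting MDS/AML from first dose to last contact, outside the TEAE window, with the follow-up time.
3. **Protocol 10.5.2, Protocol 9.3.1 and SAP 6.5.2:** use one anchor for the 30-day window.
4. **Study report:** with enrollment closed at 13, give the observation window with any statement that no MDS/AML occurred, and say that events after the window were required only if judged related.

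The cost is one question at a contact already made, one CRF field and one table line. The downside is small: some cases due to other therapy will be collected and will need a narrative on attribution. No dose or clinical rule changes.
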